13.7 Analysis of Primary Endpoints

The extent of immune cell infiltration (in the bone biopsy specimens): The comparison of an increase in CD4+ T or CD8+ T cell infiltration levels measured in the bone biopsy specimen from baseline and 8 weeks between the treatment arms will use Wilcoxon rank sum tests. The difference and the 95% confidence interval will also be provided.

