13. STATISTICAL CONSIDERATIONS

13.1 Study Design/Endpoints

This is an open label phase 2 trial that randomizes 45 mCRPC patients (2:1 ratio) to radium-223 plus pembrolizumab combination therapy or to radium-223 monotherapy. The primary objective is to compare the increase in immune CD8+ and CD4+ T cell infiltration levels from baseline to 8 weeks on treatment between the two treatment arms.

Primary Endpoint:

Difference in tissue immune cell (e.g., CD4+/8+T) infiltration in the bone metastasis biopsy specimens from baseline to 8 weeks on treatments in both the combination and monotherapy arms.

Secondary Endpoints:

- Safety and Tolerability: grade 3 or higher adverse events that are considered treatment related according to NCI CTCAE (version 4.0)
- Progression-free survival (PFS): is defined as the time from the first dose of study drug to the earlier of the first documentation of definitive disease progression [as

defined by Response Evaluation Criteria in Solid Tumors (RECIST version 1.1) and PCWG2] or death due to any cause. Participants alive without disease progression are censored at date of last disease evaluation

• Overall survival as defined in 11.1.8

Exploratory Endpoints:

- Clinical-based endpoints
 - Changes in PSA
 - PSA response: defined as decline ≥50% from baseline to 12 weeks of therapy and which has been confirmed with a second PSA at ≥ 3 weeks later
 - Time to PSA progression as defined in 11.1.9
 - Time to normalization of alkaline phosphatase (if initially elevated)
 - Time to decrease in alkaline phosphatase (if initially elevated)
 - Symptomatic skeletal events (SSEs): Rate of SSEs and time to first SSE
 - Changes in osteoblastic activity on bone scan (assessed using the quantitative SPECT/CT)
 - Changes in quality of life, pain, and analgesic use, and time to introduction of analgesics
 - Immune-based endpoints
 - Quantify the CD8, CD4, and FoxP3+ CD4 (Treg) cell infiltration in the bone biopsy specimens, and to subsequently quantify the CD8/Treg and CD4/Treg ratios
 - Change in circulating T cell clonality
 - Induction of IgG antibody response
 - Changes in PD-L1 expression and co-regulation of other immune checkpoints such as TIM-3, LAG-3, and PD-L2
 - Changes in immunosuppressive cell populations and cytokines (e.g., MDSCs, Tregs, TGF-β, and iNOS)
 - Change in serum chemokines: (e.g., CXCL9, CXCL10)

- Changes in soluble PD-L1 ([name] Lab assay)
- Genomic-based endpoints

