13.4 Sample size justification

The study plans to enroll 45 patients to ensure 36 patients to include in the primary analysis after taking into consideration that 20% patients may be lost to follow-up or have inadequate serum and tissue specimens for analysis.

The sample size justification is based on comparisons between the treatment arms of the increase in CD4+ T or CD8+T cell infiltration levels measured in the bone biopsy specimen from baseline to 8 weeks. Our primary biological hypothesis is that patients receiving pembrolizumab plus radium-223 will have a higher increase in CD8+ and CD4+ T cell infiltration from baseline to 8 weeks on treatment than patients treated with radium-223 alone. While little is known of CD8+ T cell levels in metastatic prostate cancer specimens, a 50% to 80% difference between the treatment arms for the increase in CD4+ or CD8+ T cells would represent a biologically meaningful treatment effect. With a total of 36 patients with adequate tissue/specimens for analysis, the study would provide 24 patients treated with the combination and 12 patients treated with radium-223 monotherapy. There would be 91% statistical power to detect a difference of increase in CD4/8 cell infiltration levels

between the treatment arms that is 1.2 times the population standard deviation (i.e. an effect size of 1.2, defined as the difference as a fraction of population standard deviation) using Wilcoxon rank sum test with two-sided type I error α =0.05. This corresponds to a hypothesis test for a 70% difference between the two treatment arms of the increase in CD4/8 T cell infiltration levels, with a population standard deviation (SD) of 58%. The following table provides statistical power to be achieved from a few other scenarios with effect size assumptions.

	Table 18: Statistical power for Wilcoxon rank sum test								
	Effect size								
	(Diffe	(Difference of the increase in CD4/8+ cell infiltration levels							
			between arms/	(SD)					
Evaluable		1.2							
Sample sizes	0.8	0.9	1	1.1	(=.7/0.58)				
100% enrolled									
N1=30, N2=15	69	79	86	92	96				
80% enrolled									
N1=24, N2=12	59	69	78	85	91				

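### The primary comparison covers CD4+ and CD8+ cells, but the plan gives one undivided 0.05, power for one test, and no rule for when the objective is met.

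*Combined protocol and SAP*

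**What the plan says.** The cell types are joined in three different ways.

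- **'And'.** The objective in 13.1 is "to compare the increase in immune CD8+ and CD4+ T cell infiltration levels from baseline to 8 weeks on treatment". The primary hypothesis in 13.4 expects "a higher increase in CD8+ and CD4+ T cell infiltration from baseline to 8 weeks on treatment" in the combination arm.
- **'Or'.** The sizing in 13.4 rests on comparing the arms in terms "of the increase in CD4+ T or CD8+T cell infiltration levels measured in the bone biopsy specimen from baseline to 8 weeks", and the effect called meaningful is "a 50% to 80% difference between the treatment arms for the increase in CD4+ or CD8+ T cells". The analysis in 13.7 also uses 'or', in "The comparison of an increase in CD4+ T or CD8+ T cell infiltration levels measured in the bone biopsy specimen", and speaks of rank sum tests in the plural.
- **Examples only.** The endpoint in 13.1 is "Difference in tissue immune cell (e.g., CD4+/8+T) infiltration in the bone metastasis biopsy specimens". The objective in 1.2 also introduces the cell types with 'e.g.'.

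On error and power, 13.4 states: "There would be 91% statistical power to detect a difference of increase in CD4/8 cell infiltration levels". This is for a difference of 1.2 SD, 24 versus 12 evaluable patients, and a Wilcoxon rank sum test at two-sided 0.05. Section 13.7 adds that the difference and its 95% confidence interval will be reported. No section splits the alpha, orders the tests, names one cell type as primary, defines a combined CD4/CD8 measure, or says which pattern of results meets the objective.

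**The concern.** This is the trial's only primary comparison, and it alone sets the sample size. With two cell types and no rule, a result significant for one of them could be reported as meeting the objective (following the 'or' in 13.7) or as missing it (following the 'and' in 13.4), and the choice could be made after the data are seen. The 'e.g.' leaves even the list of cell types open. The stated 5% and 91% belong to one test. Whether they describe the actual decision depends on a rule that the plan does not give.

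**Working it through.** **Inputs from 13.4.** 24 and 12 evaluable patients; effect 1.2 SD (0.70/0.58 = 1.207); Wilcoxon rank sum test; two-sided alpha 0.05.

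**Assumptions not in the documents.** Changes are normally distributed. The correlation between the CD4+ and CD8+ changes, which the plan does not give, runs from 0 to 0.9. Both cell types are tested at 0.05, which is the natural reading of the plural in 13.7 but is not stated.

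**Step 1: reproduce the plan's figure.** Use the normal approximation with the Wilcoxon efficiency 3/π.

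- Noncentrality = 1.2 × √[(3/π) × 24 × 12/36] = 1.2 × √7.639 = 3.317
- Power = Φ(3.317 − 1.960) = Φ(1.357) = 91.3%, against 91% stated
- At 0.8, 0.9, 1.0 and 1.1 SD the same formula gives 59.9%, 70.1%, 78.9% and 86.0%, against 59, 69, 78 and 85 in Table 18

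The stated power is therefore that of one test at an undivided 0.05. Simulated rank sum tests on normal data give about 89% for the same single test, so both methods are shown below.

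**Step 2: two tests, independent case by hand.**

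- Either counts, no true effect: 1 − 0.95² = 9.75%
- Both needed, 1.2 SD in each: 0.913² = 83% by the approximation; 0.89² = 79% from the simulated single-test power

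**Step 3: with correlation.** Each cell gives the approximation, then the simulation (100,000 trials per scenario), in percent.

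| Quantity | ρ = 0 | ρ = 0.5 | ρ = 0.7 | ρ = 0.9 |
|---|---|---|---|---|
| Either counts: familywise error | 9.75 / 9.5 | 9.1 / 8.8 | 8.4 / 8.3 | 7.0 / 7.0 |
| Both needed: power, 1.2 SD in each | 83.3 / 79.5 | 85.2 / 81.6 | 86.5 / 83.0 | 88.4 / 85.3 |
| Exactly one p < 0.05, 1.2 SD in each | 16.0 / 19.4 | 12.1 / 15.0 | 9.6 / 12.1 | 5.6 / 7.4 |
| Holm: at least one, 1.2 SD in each | 98.0 / 96.8 | 94.7 / 93.0 | 92.8 / 90.7 | 89.9 / 87.4 |
| Holm: at least one, only one moves by 1.2 SD | 86.2 / 82.6 | 86.6 / 83.0 | 86.9 / 82.9 | 87.1 / 83.2 |

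The third row shows how often the missing rule would decide the conclusion on the plan's own effect assumption: about 6% to 19% of trials, depending on correlation and method.

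**The case against.** The strongest reply is that little depends on this p-value. The trial is a 45-patient phase II study, 13.12.2 says that there is no primary efficacy endpoint, no passage ties a go/no-go decision to the test, and 13.7 reports the difference with an interval. All of this stands, and it limits the severity. It does not supply a success rule: the plan chose a formal hypothesis, alpha and power, and these should match the decision made.

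A second reply is that 'or' may mean only 'for each cell type', and that the one written hypothesis requires both. That is a fair reading. It controls the error at 5%, but 91% then overstates the power. A third is that 'CD4/8' means one combined measure, but no section defines one.

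A reader might go further and infer that the type I error is inflated. The documents do not support that as a flat statement: it follows only if either result counts, and no passage says so. Even then, the chance of a false claim of an increase is about half the familywise figure, roughly 4.9% to 3.5% against 2.5% for one test.

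A reader might also infer that the same comparison is listed twice, because the exploratory endpoints in 13.1 include "Quantify the CD8, CD4, and FoxP3+ CD4 (Treg) cell infiltration in the bone biopsy specimens". That item leads on to the ratios to Treg cells, and the power in Table 20 (13.10) is for change within Arm A. These are largely different analyses of the same measurements, so the point is not made here.

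**Conclusion.** The concern holds in this form: the plan has two cell types, one undivided alpha, power for one test and no success rule, so the stated 5% and 91% do not both hold for a decision on two cell types each tested at 0.05. If either counts, familywise error is about 7% to 9.75%. If both are needed, power is about 79% to 85% simulated, or 83% to 88% by the plan's approximation. These figures rest on 24 versus 12 evaluable patients, normal changes, correlation 0.9 to 0 for the error and 0 to 0.9 for the power and, for power, 1.2 SD in both cell types.

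The 91% is not an arithmetic error for a single test, and nothing here shows the sample size to be invalid. The plan should be corrected, but in a phase II biomarker comparison this falls short of a critical defect.

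**What to change.** Before any biopsy results are compared by arm, remove 'e.g.' and use one wording in 1.2, 13.1, 13.4 and 13.7. Add one sentence stating when the primary objective is met, and restate the power for that rule, labelled by method and assumed correlation.

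The rule closest to the written hypothesis is that both cell types must be significant at two-sided 0.05, with power restated as about 79% to 85% (simulated rank sum tests, correlation 0 to 0.9, 1.2 SD in each).

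Two alternatives are also acceptable. The documents give no basis for ranking them, so the choice is the sponsor's.

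- **Holm at overall two-sided 0.05.** Simulated power is about 97% to 87% for at least one cell type if both move, and about 83% if only one moves.
- **One named cell type as the single primary, the other secondary.** The 0.05 stands. Power is 91% by the plan's approximation and about 89% simulated.

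The cost is wording in four sections and no more patients. Requiring both makes the stated power less favourable. Holm lowers it when only one cell type moves or when the correlation is high. With a single primary, an effect confined to the other cell type would not be detected by the primary test beyond its 5% error rate.

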13.3 Stratification Factors

Patients will be stratified based on:

- Baseline alkaline phosphatase <220 or ≥ 220
- Volume of bone metastases (high: ≥ 4 bone metastases including one beyond the axial skeleton vs. low: <4 bone metastases)
 Based on CHAARTED (ECOG 3805) criteria²⁴

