13.8 Analysis of Secondary Endpoints

Safety and Tolerability: All adverse events recorded during the trial will be summarized for the safety population. The incidence of events that is new or worsening from the time of first dose of treatment will be summarized according to system organ class term, severity (based on CTCAE version 4.0 grade), type of adverse event, and relation to study treatment. For the combination therapy, special interests include toxicities related to induction of immune phenomenon such as pneumonitis, colitis, and severe rash. The frequency of AEs will be summarized separately according to treatment arms, with 90% exact binomial confidence intervals (CI). The proportion of patients in each arm with grade 4 or higher AEs will also be reported with an exact binomial 90% CI.

Deaths reportable as SAEs and non-fatal serious adverse events will be listed by patient and tabulated by primary system organ class, and type of adverse event.

PFS and OS: The distributions of time to PSA progression, PFS and OS will each be summarized using the product-limit method of Kaplan-Meier according to treatment arms. Median times for each endpoint will be presented with two-sided 95% confidence intervals estimated using log(-log(survival)) methodology. Kaplan-Meier estimates of the endpoints at 6 or 12 months after treatment initiation may also be presented with two-sided 95% confidence intervals.

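### The primary rank sum test leaves out the two randomization strata; if they predict the change in infiltration, it is conservative and gives up some power

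*Combined protocol and SAP*

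**What the plan says.** Section 13.3, repeating section 5.1, sets the strata under "Patients will be stratified based on": baseline alkaline phosphatase cut at 220, and bone-metastasis volume, high or low. Two binary factors give four strata.

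The primary comparison in section 13.7 is unstratified: the increase in CD4+ T or CD8+ T cell infiltration "from baseline and 8 weeks between the treatment arms will use Wilcoxon rank sum tests". A difference with a 95% confidence interval is promised, and no adjustment is named for it.

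The power basis in section 13.4 matches that test: "using Wilcoxon rank sum test with two-sided type I error" of 0.05, "24 patients treated with the combination and 12 patients treated with radium-223 monotherapy", "an effect size of 1.2, defined as the difference as a fraction of population standard deviation", and a 70% difference "with a population standard deviation (SD) of 58" percent. The result is stated as "There would be 91% statistical power to detect a difference of increase in CD4/8 cell infiltration levels".

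PFS and OS in section 13.8 "will each be summarized using the product-limit method of Kaplan-Meier according to treatment arms", with no between-arm test. The only mention of adjustment for covariates in section 13 is in the optional quality-of-life mixed models of section 13.9, which refer to relevant factors without naming these two.

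**The concern.** Stratified randomization makes the arms alike on the stratifying factors, so the treatment contrast varies less from one hypothetical trial to the next. A test that ignores the factors still judges the contrast against the full variance. If the factors predict the outcome, its true type I error lies below 5% and it has less power than a test that uses them.

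The stakes are modest but not empty. Table 18 gives the planned test 59% power at effect size 0.8 and 69% at 0.9 with 24 against 12 patients. Section 13.4 regards differences from 50% to 80% as biologically meaningful. On the plan's SD, the lower end is 50/58 = 0.86 SD, in the part of Table 18 where power is weakest. Each outcome value costs a patient two bone biopsies.

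**Working it through.** **Inputs from the documents.** Two-sided alpha 0.05; 24 and 12 evaluable patients of 45 enrolled (2:1, 20% loss); effect size 1.2 = 70/58 (1.207); SD 58%, described as a population SD; two binary strata (sections 5.1, 13.3, 13.4).

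**Inputs assumed.** The share of outcome variance explained by the two factors (R²) is not given, so 0 to 0.5 was tried. Also assumed: permuted blocks of 3 within strata, two equally strong additive factors each split 50/50, normal outcomes, and 9 of 45 patients lost at random.

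**Step 1: the plan's own figures.** Enrolment: 36/(1 − 0.20) = 45, as stated. Power by the normal formula: 1.2 × √(24 × 12/36) = 1.2 × √8 = 3.394; 3.394 − 1.960 = 1.434; power 92.4%. With the Wilcoxon efficiency 3/π: 1.2 × √(8 × 0.955) = 3.317; 3.317 − 1.960 = 1.357; power 91.3%. Noncentral t gives 90.9%, or 89.6% with 3/π. Direct simulation of the test (40,000 runs) gives 88.9%. The stated 91% is reproduced.

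**Step 2: mechanism.** With perfect balance in all strata, the true variance of the contrast is (1 − R²) times the variance the plain test assumes. Its size is then about 2Φ(−1.96/√(1 − R²)).

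- R² = 0.1: 1.96/0.949 = 2.066, size 3.9% (simulated 4.0%)
- R² = 0.2: 1.96/0.894 = 2.191, size 2.8% (simulated 2.5%)
- R² = 0.3: 1.96/0.837 = 2.343, size 1.9% (simulated 1.9%)

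Under simple, unstratified randomization the simulated size at these three values is 5.1%, 5.1% and 4.8%. The conservatism therefore comes from the stratified balance.

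**Step 3: the realistic design.** Stratified blocks of 3 with random loss keep the balance only in part. The comparator is a least-squares model of the ranks on arm and the two factors (36 − 4 = 32 residual degrees of freedom). There were 6,000 runs under the null and 3,000 per alternative, without continuity correction. Cells show plain test / rank model, in %.

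| R² | Type I error | Power, effect 1.2 | Power, effect 0.8 |
|---|---|---|---|
| 0 | 4.8 / 5.0 | 88.0 / 87.9 | 56.3 / 56.0 |
| 0.1 | 4.1 / 4.8 | 89.2 / 91.0 | 56.0 / 60.0 |
| 0.2 | 3.7 / 5.4 | 91.3 / 94.9 | 57.1 / 65.5 |
| 0.3 | 2.6 / 4.9 | 90.1 / 95.8 | 55.7 / 69.8 |
| 0.5 | 1.2 / 4.9 | 92.4 / 99.3 | 54.8 / 81.7 |

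Simulation error is about 0.3 points on size and 0.5 to 0.9 points on power.

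A second set of 6,000 runs, with the continuity correction, also covered effect 0.9:

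- R² = 0: 87.7 / 87.8 at effect 1.2
- R² = 0.1: 89 / 92 at 1.2 and 67 / 71 at 0.9
- R² = 0.2: 89 / 94 at 1.2 and 67 / 76 at 0.9, with size 3.0 / 4.8

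A further check at R² = 0.2 gave 65.4 / 74.9 at effect 0.9 and size 2.9 / 4.8. With 75% of patients in one level of each factor, power at effect 0.8 and R² = 0.2 was 55.3 / 64.9, so equal strata do not drive the result.

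**Step 4: choice of adjusted test.** A van Elteren test over the four strata has 83.6% power at effect 1.2 when R² = 0, against 88.0% for the plain test, a cost of about 4 points. At R² = 0.1 it has 88.0% against 89.2%. It is ahead only by R² = 0.2 (92.3% against 91.3%), and it trails the rank model throughout.

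**The case against.** The strongest reply is that nothing in the documents links alkaline phosphatase or metastasis volume to the change in T-cell infiltration. Section 13.4 itself admits that little is known about CD8+ levels in these specimens. If R² is 5%, the gain is 0.9 points at effect 1.2 (88.8% against 89.7%) and 1.9 points at 0.9. Sizeable losses need R² of 20% or more. This stands: the consequence is conditional and its size is an assumption.

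It also stands that the primary population in section 13.6 is selected after randomization, on having both biopsies, so the balance that causes the conservatism is only partly kept. The simulation allows for loss at random, but not for loss related to stratum or outcome.

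Three stronger readings are tempting, and the documents do not support them.

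- A reader might infer that the 91% is wrong. It is not. The SD of 58% is a population SD, which already contains the variation between strata, and in the first simulation set the planned test keeps 88% to 92% power at effect 1.2 for every R² tried.
- A reader might infer that stratifying was wasted. It still guards against chance imbalance, whatever the analysis.
- A reader might want a stratified Cox model for PFS and OS. Section 1.3 frames efficacy as preliminary, and section 13.8 plans descriptive curves. With 15 control patients over four strata (15/4, about 4 each), such a model would meet the same sparse cells that count against van Elteren.

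The reply does not remove the point itself, because in these simulations adjusting by main effects cost nothing measurable when the factors do not matter.

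**Conclusion.** The point holds as an available gain in efficiency. If the strata explain 10% of the variance in the change in infiltration, the planned test gives up about 2 to 3 points of power at effect 1.2 and about 4 at 0.9. At 20% it gives up about 4 and 9 points, and its size falls to roughly 3% to 4%. At zero nothing is lost. These figures rest on the assumed R², blocks of 3, equal strata, normal outcomes and random loss of 9 patients. The plan's validity is not in question: any departure from the nominal type I error is downwards, and the sample size agrees with the test it names. The change is worth making because the possible gain is material at the smaller effects and the downside is close to nil.

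**What to change.** In section 13.7, before any outcome data are seen:

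- Make the primary test a linear model of the ranks of the increase on arm, alkaline phosphatase stratum and bone-volume stratum as main effects, with strata as recorded at randomization. Apply it in the same way to CD4+ and CD8+.
- Keep the plain rank sum test as a named sensitivity analysis.
- Take the promised difference and 95% CI from a linear model of the increase itself with the same two factors, since an arm effect in rank units cannot be read as a difference in infiltration.
- Do not use a van Elteren test over four small strata.

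In sections 5.1 and 13.3, reconcile the volume definition. The high level needs four or more metastases with one beyond the axial skeleton, and the low level needs fewer than four. A patient with four or more, all axial, fits neither. Such patients must fall in one stated level, and the level used at randomization should be documented.

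Sections 13.8 and the PFS and OS summaries need no change on this account. The cost is a few sentences of SAP text and two degrees of freedom; the factors are already recorded at randomization.

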Analyzing tumor derived cf-DNA in the blood can potentially circumvent the above challenges. cf-DNA is composed of fragments of coding and non-coding DNA which are released into the circulation during tumor cell apoptosis or necrosis.43 Previous studies have shown that compared to normal controls, patients with prostate cancer have significantly higher levels of cf-DNA.⁴⁴ High pretreatment levels of tumor derived cf-DNA have been associated with poor response to taxane chemotherapy and worse clinical outcomes.⁴⁵ In addition to quantitative changes, cf-DNA has the potential to establish pretreatment mutational signatures that may predict resistance or sensitivity to established and investigational therapies. Supporting this concept, Salvi et al demonstrated that pretreatment copy number gain in AR and CYP17A1 genes detected in cf-DNA samples was predictive of poor overall survival and progression-free survival (PFS).⁴⁶ Further, by comparing the genomic alterations at baseline, on treatment, and at the time of disease progression, it may be possible to uncover novel mutations, copy number alterations and somatic variants which can be acquired as a result of clonal evolution and lead to treatment failure.^{47,48} A major advantage of cf-DNA is that the sample is obtained by a simple blood draw and does not require a more invasive tumor biopsy.

Whole genome sequencing of circulating tumor derived cell free DNA

Blood samples will be obtained from patients enrolled in both arms prior to treatment initiation (week 1), on therapy at week 5 and week 13, and at the time of disease progression. Whole genome sequencing will be performed at 0.1x coverage, which we term ultra-low pass whole genome sequencing (ULPWGS). The sequencing information derived from ULPWGS will be used to estimate "tumor purity", which is defined as percent of circulating DNA derived from tumor cells in the blood, and to identify copy number alterations in the tumor using an adaptation of a probabilistic model, called ichorCNA.⁴⁹ While other algorithms for assessing copy number changes from cf-DNA have been described,^{50,51} ichorCNA has the advantage of accounting for mixtures of cell populations to assess for subclonal events and estimating tumor purity.

As this study was added during study enrollment, not all patients will have cfDNA analysis performed. Lack of cfDNA samples will not be considered a deviation.

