13.6 Definition of Analysis Populations

Safety population: All patients who have received at least one dose of radium-223 or pembrolizumab will be included in safety assessment.

Primary analysis population: All patients who receive at least one dose of radium-223 and if in arm A, one dose of pembrolizumab and have bone biopsy assessment at baseline and 8 weeks will be included to assess primary, secondary, and exploratory endpoints.

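### The primary Wilcoxon test on the increase is valid, but it does not use as a covariate the baseline biopsy value that every analysed patient has

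*Combined protocol and SAP*

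**What the plan says.** Section 13.7 compares the increase in CD4+ or CD8+ infiltration from baseline to 8 weeks between the arms; the comparison "between the treatment arms will use Wilcoxon rank sum tests". It adds: "The difference and the 95% confidence interval will also be provided". It names no covariate and does not say how the interval is obtained.

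Section 13.6 limits the primary analysis to treated patients who "have bone biopsy assessment at baseline and 8 weeks". Baseline therefore enters the primary test only by subtraction. Within section 13, model adjustment for other factors is mentioned only for the exploratory quality-of-life mixed models in 13.9.

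Section 13.4 powers the same test: 24 versus 12 evaluable patients, two-sided 0.05, effect size 1.2 (a 70% difference over an SD of 58%), power 91%. It treats "a 50% to 80% difference between the treatment arms for the increase in CD4+ or CD8+ T cells" as biologically meaningful and says that little is known about CD8+ levels in this tissue. Table 18, titled "Statistical power for Wilcoxon rank sum test", gives 59% at effect 0.8 and 69% at 0.9 for these numbers.

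**The concern.** Only 36 evaluable patients carry the primary question, each at the price of two bone biopsies. The lower end of the plan's own meaningful range is 0.50/0.58 = 0.86 SD, where the planned test has about 63% power. Table 18 already shows this level of power, so nothing is hidden. In such a small trial, though, a baseline measurement available for everyone is worth using if it explains part of the variation in change. Subtracting baseline does not do this in general: change is usually still correlated with baseline, and an unadjusted test leaves that variation in the noise.

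**Working it through.** **1. The plan's figure.** Inputs from 13.4: n = 24 and 12, two-sided 0.05, effect 1.2 (0.70/0.58 = 1.207). Noncentral t with 34 df: noncentrality = 1.2 × √(24×12/36) = 1.2 × 2.828 = 3.39, power 90.9% (91.2% at 1.207). Simulated Wilcoxon on normal data: 88.9% at 1.2 and 89.4% at 1.207. The stated 91% is reproduced within about 2 points. The simulated two-sided error rate of the Wilcoxon is close to 5%, so it is valid.

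**2. When adjustment can help.** Let r be the baseline to week-8 correlation and k = week-8 SD / baseline SD. Then

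corr(change, baseline) = (r·k − 1) / √(1 + k² − 2·r·k).

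This is zero when r = 1/k, and there is then nothing to gain. For k = 1 and r = 0.6: (0.6 − 1)/√0.8 = −0.45. For k = 1.5 and r = 0.6: (0.9 − 1)/√1.45 = −0.08. The documents give neither r nor the SDs at each visit, so everything below is a range under assumptions.

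**3. Power with a common baseline slope.** Normal data, 24 versus 12, effect in SDs of change, 60,000 simulated trials per cell. The adjusted test regresses the rank of change on arm and the rank of baseline, with the usual t reference.

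| Absolute correlation of change with baseline | Wilcoxon, 0.86 | Adjusted, 0.86 | Wilcoxon, 1.2 | Adjusted, 1.2 |
|---|---|---|---|---|
| 0 | 62.5% | 61.9% | 89.0% | 88.3% |
| 0.15 | 63.0% | 63.1% | 89.0% | 88.9% |
| 0.3 | 62.7% | 65.6% | 89.0% | 90.9% |
| 0.5 | 63.1% | 73.1% | 89.0% | 94.6% |
| 0.6 | 63.1% | 79.0% | 89.2% | 97.1% |

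Break-even is near 0.15. With no treatment effect, the Wilcoxon rejects in 4.6 to 5.0% of trials and the adjusted test in 4.9 to 5.2%.

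**4. What this is worth in patients.** Simulated Wilcoxon power at effect 0.86 and 2:1 allocation is 62.7% for N = 36, 66.5% for 39, 70.1% for 42, 73.4% for 45 and 79.0% for 51. By interpolation, 65.6% corresponds to 36 + 3 × (2.9/3.8) ≈ 38 patients. A correlation of 0.5 corresponds to about 45 and 0.6 to about 51.

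**5. Why ranks.** With heavy-tailed errors (t, 3 df), zero correlation and effect 0.8, unranked ANCOVA has 67.0% power against 81.1% for the Wilcoxon. Rank adjustment still costs under 1 point.

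**6. Unequal slopes.** Keep the distribution of change identical in both arms (variance 1), with slope −0.6 in combination and 0 in control. The common slope is about (2/3)(−0.6) = −0.4.
- Residual variance, combination: 0.64 + 0.2² = 0.68. Control: 1 + 0.4² = 1.16.
- Pooled: (24×0.68 + 12×1.16)/36 = 0.84.
- Variance of the arm difference assumed by the model: 0.84 × (1/24 + 1/12) = 0.105. Actual: 0.68/24 + 1.16/12 = 0.125.
- Actual level: P(|Z| > 1.96/√(0.125/0.105)) = P(|Z| > 1.80) ≈ 7.2%.

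Simulation of the rank-adjusted test gives 7.0 to 7.1%, against 4.9% for the Wilcoxon. With the slopes exchanged (0 in combination, −0.6 in control), the same steps give assumed 0.120 and actual 0.110, so a level of about 4.1% (simulated 4.2%). On power, slopes of opposite sign (0.3 in control, −0.3 in combination) at effect 1.207 give 88.6% adjusted against 89.3%; the largest loss found in any unequal-slope case was 1.1 points (61.2% to 60.1%).

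**The case against.** The case for leaving 13.7 alone is fair. The planned test is valid, is the one that was powered, and is an ordinary choice for 36 patients. The benefit depends wholly on a correlation that the documents do not give; at the design effect it is only about 2 points at 0.3. All of this stands, and it keeps the point at the level of an improvement.

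Three stronger readings are tempting and should not be drawn.

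A reader might infer that adjustment is free and always keeps the 5% level. That holds only with a common baseline slope. Unequal slopes are not far-fetched: the rationale in 2.3 has PD-1 blockade reversing anergy of infiltrating immune cells, so response could depend on the infiltrate already present. Slopes are equal when treatment affects no patient, so the no-effect null is safe, and a permutation p-value protects it directly. It does not protect the weaker null of equal average change with different slopes.

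A reader might infer that this protocol version was written during enrolment, because 9.5 says: "As this study was added during study enrollment, not all patients will have cfDNA analysis performed". That sentence dates only the cfDNA sub-study. Enrolment and biopsy-reading status at the November 2019 version are not given.

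A reader might also infer that adjustment settles how CD4+ and CD8+ share the 5%. It neither creates nor cures that question, which is separate.

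**Conclusion.** The point holds as a low-cost gain in efficiency. At effect 0.86, with a common slope and normal data, power rises from about 63% to about 66%, 73% or 79% at absolute correlations of 0.3, 0.5 or 0.6; there is no gain below about 0.15, and the cost at zero is about 0.6 point. Every correlation is an assumption. If slopes differ between arms, the gain shrinks or becomes a loss of about 1 point, and the model-based level can lie between about 4% and 7%. The power figures use the t reference; the permutation version was not simulated.

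**What to change.** In 13.7:

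1. State one scale for the increase and use the same scale for baseline.
2. Primary test: regress the rank of change on arm and the rank of baseline, two-sided 0.05. Obtain the p-value by permuting arm, within the randomisation strata of 13.3, so that the no-effect null is protected.
3. Take the difference and 95% interval from the same test, as all shifts d for which the test on change minus d × arm does not reject. With the model-based p-value this gave no conflict between interval and test in 9,000 simulated trials and coverage of about 95%; pairing the rank test with an ordinary ANCOVA interval conflicted in 7 to 8%.
4. Keep the planned Wilcoxon as a sensitivity analysis.
5. State the common-slope limitation and report the baseline slope in each arm.
6. Record the change, dated and with its reason, before any comparative biopsy data are seen. The trial is open label, so first confirm what has been read and by whom. If the change can no longer be made blind to the data, leave the Wilcoxon as primary and present the adjusted analysis as supportive.

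The cost is one degree of freedom, a dated amendment and short programming, plus the small losses given above if the correlation is near zero or the slopes differ. No new data are needed.
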